Study Protocol and Statistical Analysis Plan

Official Title:

The Effect of the Flipped Classroom Model on Nursing Students' Pediatric Pain Management Knowledge and Learning Motivation: A Randomized Controlled Trial (FLIPNURSE)

Unique Protocol ID:

ErsoyU-[name]-FC2022

NCT Number:

Pending (to be assigned)

Sponsor/Collaborators:

Faculty of Health Sciences, Burdur Mehmet Akif Ersoy University

Principal Investigator:

[name], Assistant Professor

Version/Date:

Version 1.0 — August 31, 2021

The Effect of the Flipped Classroom Model on Nursing Students' Pediatric Pain Management Knowledge and Learning Motivation: A Randomized Controlled Trial Abstract

Aim

The aim of this study is to evaluate the effect of the flipped classroom model on nursing students' knowledge level and learning motivation in pediatric pain management.

Background

Pain management in children is an important and multidimensional responsibility in nursing. However, the time allocated to pediatric pain and the opportunities for practical application in nursing education programs are limited. The integration of active learning approaches is necessary to increase knowledge and motivation in this area.

Design

This study is a parallel-group, randomized controlled experimental study conducted at a state university in Turkey.

Methods

A total of 84 third-year nursing students were randomly assigned to an intervention (n=42) and control (n=42) group. The intervention group was taught using the flipped classroom model, while the control group was taught using the self-directed learning model. Data were collected at three time points (pre-test, post-test, and 3 months post-intervention) and analyzed using a two-way mixed-design ANOVA.

Results

At baseline, there were no significant differences between the groups in terms of knowledge and motivation levels (p > 0.05). After the training, significant and sustainable increases were observed in both variables in the intervention group (p < 0.001), while no significant changes were observed in the control group.

The group × time interaction was found to be significant for both variables, indicating that the flipped classroom model provides an effective and sustainable contribution to knowledge level and motivation.

Conclusions

Flipped classroom-based instruction emerges as an effective method for enhancing nursing students' knowledge level and learning motivation in pediatric pain management. The integration of this model into nursing education programs is recommended.

Key words: Pediatric Pain Management; Flipped Classroom; Nursing Students; Learning Motivation; Randomized controlled trial

1. Introduction

Pain management in children is an important nursing responsibility that involves not only physiological but also psychological and ethical dimensions. Children hospitalized in hospitals frequently experience pain due to medical interventions, surgical procedures, and chronic diseases (Shah & Siu, 2019). These pain experiences can lead to short-term physiological changes as well as psychological responses such as anxiety and restlessness (Shanmugam et al., 2025). In the long term, they can result in serious consequences such as behavioral disorders, sleep problems, and chronic pain (WHO, 2020).

The assessment and management of pain in pediatric patients is a more complex process compared to adults. This complexity stems from children's pain perception, which varies according to developmental stages, limited verbal expression skills, and individual differences (Shah & Siu, 2019; Kudubeş, Bektaş & Bektaş, 2021). Research indicates that nurses and nursing students have insufficient knowledge and skills regarding pediatric pain management (Ekim & Ocakcı, 2013; Alshehri et al., 2024; Ülgen & Tüfekci, 2024; Shanmugam et al., 2025). This situation is considered an important risk factor that may negatively affect the quality of care for pediatric patients. Therefore, organizations such as the International Association for the Study of Pain (IASP) and the World Health Organization (WHO) are working to increase global awareness of pediatric pain management. Particularly in low- and middle-income countries, they have called for international action to strengthen education in this field (Bond, 2011; Raja et al., 2020).

Nursing students can develop effective pain management skills through a qualified and comprehensive education process (Yuan, 2024). However, the time and resources allocated to pediatric pain management in current nursing programs are insufficient. In particular, limited opportunities for practical training negatively affect students' clinical competence (Ung et al., 2016). This situation may lead to significant deficiencies in future nurses' ability to recognize, assess, and manage pain. Therefore, the integration of alternative teaching methods that deepen learning, increase motivation, and enhance practical skills into the education system is no longer an option but a necessity (Shamsi, 2025).

The flipped classroom model is an innovative teaching approach that supports students in taking a more active role in the learning process and is increasingly accepted in educational sciences (Busebai et al., 2021; Barranquero-Herbosa, Abajas-Bustillo, & Ortego-Maté, 2022). This model is based on students learning theoretical knowledge outside the classroom through online

content and dedicating classroom time to application-based learning activities (Shi et al., 2025; Zhang et al., 2025). Current research in health sciences shows that the flipped classroom approach has positive effects on students. It has been reported that this approach significantly improves students' academic achievement, learning motivation, and critical thinking skills (Betihavas et al., 2016; Liu et al., 2018; Xu et al., 2019; Sureda-Negre, Comas-Forgas & Morey-López, 2019; Merrou et al., 2023; Alshehri et al., 2024).

However, a review of the literature reveals that no randomized controlled trial has yet been conducted to evaluate the effectiveness of the flipped classroom model in the field of pediatric pain management. Current systematic reviews and meta-analyses clearly emphasize that randomized controlled studies on the reverse class approach have primarily focused on general nursing practices or general pediatrics topics; no direct randomized controlled study specifically addressing pediatric pain management has been identified. (Barranquero-Herbosa, Abajas-Bustillo, & Drtego-Maté, 2022; Shi et al., 2025). This gap in the literature highlights the need for empirical studies evaluating the impact of pedagogical innovations in nursing education. This study aims to address this need by examining the effect of the flipped classroom model on nursing students' knowledge level and learning motivation in pediatric pain management.

Research Hypotheses

Hypothesis 1: The pediatric pain knowledge scores of students educated with the flipped classroom model are significantly higher than those of the control group.

Hypothesis 2: The learning motivation scores of students educated with the flipped classroom model are significantly higher than those of the control group.

2. Methods

2.1. Design and Settings

This study was designed as a parallel group randomized controlled trial. The study was conducted with third-year students enrolled in the Nursing Department of a state university in Turkey. The implementation process began in February 2022 and was completed in July 2022. The study was completed according to the planned schedule; there were no interruptions in the education and follow-up processes. No changes were made to the planned methodological approaches during the research process. The research design, measurement timelines, sample criteria, and analysis methods remained consistent throughout the study.

2.2. Instruments

Research data were collected using an individual identification form, a pediatric pain management knowledge scale for nursing students, and a motivation survey regarding teaching materials.

2.2.1. Individual Identification Information Form

This form was prepared by the researchers to assess the demographic characteristics of the students and their self-efficacy perceptions regarding pediatric pain management (Gadallah et al., 2017; Aydın & Dektaş, 2020; Liu et al., 2020).

2.2.2. Pediatric Pain Management Knowledge Scale

This scale was developed by Aydın and Bektaş (2021) to measure nursing students' knowledge levels regarding pediatric pain (Aydın and Bektaş, 2021). High scores on this 5-point Likert scale, consisting of six subdimensions and 29 items, indicate higher knowledge levels. The subscales of the scale include pain awareness with 6 items (items 1, 2, 3, 4, 5, and 29), pain pathophysiology (items 6, 7, 25, and 26), barriers to pain management (items 8, 9, 10, 11, 12, 13, 14, 15, 16, 17, and 18), pain diagnosis 2 items (19 and 20), pain assessment 2 items (20 and 21), and pain control 4 items (23, 24, 27, and 28). The coding of items 3, 6, 8, 10, 11, 12, 13, 14, 15, 17, and 21 in the scale has been reversed. The scale has a minimum score of 29 and a maximum score of 145, with higher scores indicating that students have more knowledge about Pediatric Pain Management. The reliability coefficient of the scale is 0.864. In this study, the Cronbach's alpha coefficient of the scale was calculated as 0.845.

2.2.3. Motivation Questionnaire Regarding Teaching Materials

The Teaching Material Motivation Survey (ÖMMA) was developed by Keller and its validity and reliability were studied in Turkish by Kutu and Sözbilir (Keller, 2006; Kutu & Dir, Sözbilir, 2011). This scale, which aims to determine students' motivation levels toward instructional materials, consists of a total of 24 items on a 5-point Likert scale. The items in the attention-appropriateness dimension of the ÖMMA are 1, 2, 3, 4, 5, 6, 7, 8, 9, 10, and 11; while the items in the confidence-satisfaction dimension are 12, 13, 14, 15, 16, 17, 18, 19, 20, 21, 22, 23, and 24. Five items in the questionnaire (3, 12, 14, 16, 18) were reverse-coded. The minimum score in the questionnaire is 24, and the maximum score is 120. A high score on the survey indicates high motivation regarding the teaching material. The Cronbach's alpha coefficient is 0.83. In this study, the Cronbach's alpha value was found to be 0.789.

2.3. Sample, randomization, and prevention of bias

The population of this study consisted of a total of 152 third-year nursing students enrolled in the Child Health and Nursing course. Sample size and power analysis were performed using the G*Power 3.1.9 program. Considering the research design (three measurements and two groups), the following parameters were used for the ANOVA test in repeated measurements: $\alpha = 0.05$, power $(1-\beta) = 0.80$, and moderate effect size (f = 0.25). Accordingly, a minimum of 27 participants per group and a total of at least 54 participants were required. Considering potential data losses, the study was conducted with 44 participants in each group (Cohen, 2013; Faul et al., 2009).

Students were divided into two groups using stratified sampling based on their academic achievement levels. Those with an academic grade point average between 2.00 and 3.00 formed the first stratum, while those with a grade point average between 3.01 and 4.00 formed the second stratum. Within each stratum, participants were assigned to either the intervention or control group in equal numbers using a computer-assisted simple random assignment method with blind allocation. The randomization process was conducted by an independent biostatistician not involved in the study, and no blocking randomization or other restriction methods were used.

The study's sampling process, group distribution, randomization, follow-up, and number of samples analyzed are presented in Figure 1 in accordance with the CONSORT 2010 guidelines. Statistical analysis and reporting were performed by an independent statistician. Since the intervention was directly integrated into the students' educational process in this study, blinding could not be applied from the perspective of the participants (students) and the researchers who administered the intervention. However, to minimize bias, blinding was ensured during the data analysis process. In this context, a data set that did not contain information about which intervention the groups received, but was only coded (e.g., Group A, Group B) and anonymized, was presented to the independent statistician; the statistician conducted the analyses without knowing the identity of the groups. Thus, objectivity was maintained and the risk of systematic bias was reduced during the analysis and reporting stages. Additionally, a chi-square test based on academic achievement scores was conducted to assess the homogeneity of the groups at the baseline level, and it was determined that the groups were at a similar level (Table 1).

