2.10. Data analysis

Data analysis was performed using IBM SPSS 25.0 (IBM Corp., Armonk, NY, USA). The assumption of normal distribution was evaluated using the Kolmogorov–Smirnov test and supported by skewness and kurtosis values within the ± 2 range. The internal consistency of the scales was determined using Cronbach's alpha coefficient.

Within the scope of statistical analysis, frequency distributions and descriptive statistics were calculated; independent samples t-test and chi-square test were used for intergroup comparisons. Two-Way Mixed ANOVA was applied to examine the effects of group, time, and group × time interaction on education. All necessary assumptions (e.g., normal distribution,

variance homogeneity, sphericity) were tested and found to be met in this analysis. The significance level was set at p<0.005 for all statistical analyses. Additionally, no subgroup analyses were conducted for variables such as age, gender, or academic achievement. All analyses were designed to focus on between-group comparisons.

3. Results

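### The 54-student minimum does not say which ANOVA term, correlation or sphericity value it rests on, and it uses a different alpha from the analysis; for a group main effect it would fall short of 80% power

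*Combined protocol and SAP*

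**What the plan says.** Section 2.3 describes the calculation as follows: "Considering the research design (three measurements and two groups"), "the following parameters were used for the ANOVA test in repeated measurements", namely alpha 0.05, power 0.80 and a "moderate effect size (f = 0.25"). From these it concludes that "a minimum of 27 participants per group and a total of at least 54 participants were required". It then adds: "Considering potential data losses, the study was conducted with 44 participants in each group". It gives no correlation among the repeated measures and no nonsphericity correction, and does not say whether the between, within or interaction term was powered.

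Hypothesis 1 (Research Hypotheses) reads: "The pediatric pain knowledge scores of students educated with the flipped classroom model are significantly higher than those of the control group". Section 2.10 names a two-way mixed ANOVA with group, time and group-by-time effects, says that all analyses focus on between-group comparisons, reports the sphericity assumption as met, and states: "The significance level was set at p<0.005 for all statistical analyses".

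**The concern.** In a repeated-measures ANOVA, the sample size for a given f depends strongly on rho, and in opposite directions for the two candidate terms. A higher rho raises the number needed for the group main effect and lowers it for the interaction. A figure given without the term and without rho cannot be checked or interpreted.

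The values of rho that return 54 are close to zero, which is unexpected for three scores from the same student on the same scale. If Hypothesis 1 is tested by the group main effect, 80% power would not be delivered at a realistic rho. The analysis threshold is also ten times stricter than the alpha in the calculation, so the stated power does not describe the test as written in section 2.10.

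**Working it through.** **Inputs.** f = 0.25, alpha 0.05, power 0.80, k = 2 groups and m = 3 measurements (section 2.3). Epsilon = 1 is an assumption, consistent with the sphericity statement in section 2.10. Rho is not stated, so a range is examined.

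**Formulas (noncentral F).**
- Group effect: lambda = f² · N · m / (1 + (m − 1)·rho), with df 1 and N − 2.
- Interaction: lambda = f² · N · m / (1 − rho), with df 2 and 2(N − 2).

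**Reproducing 54 at alpha 0.05.**
- Interaction, rho = 0: lambda = 0.0625 × 54 × 3 = 10.125, power 0.809, and 54 is the smallest even N. At rho 0.05 the answer is already 52.
- Group effect, rho = 0.10: lambda = 10.125 / 1.2 = 8.44, power 0.813, and 54 is again the smallest even N. It stays so up to rho of about 0.12; at rho = 0 the answer is 44.

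**Number analysed.** For knowledge, partial eta squared is F / (F + error df). With error df 82 this is 16.789 / 98.789 = 0.170, as reported; with 86 it would be 0.163. The F tests therefore rest on 84 students, although Tables 2 and 3 are headed n=44 per group.

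**Rho implied by the results.** With N = 84, the between-subject error mean square estimates s²(1 + 2·rho) and the within-subject one s²(1 − rho), where s² is the average of the six reported variances.
- Knowledge (Table 2), s² = 382.7. Group means averaged over time are 92.07 and 78.19, so the group mean square is (84 × 3 / 4) × 13.88² = 12,137. Dividing by F = 16.789 gives 722.9, and rho = (722.9 / 382.7 − 1) / 2 = 0.44. The interaction mean square is 4,475.3; dividing by F = 27.834 gives 160.8, and rho = 1 − 160.8 / 382.7 = 0.58. The time F gives almost the same error term (160.7).
- Motivation (Table 3), s² = 174.1. The same steps give error mean squares of 394.4 and 104.6, and rho of 0.63 and 0.40.

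**Power at alpha 0.05.**

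| rho | Group: power at 54 | Group: N for 80% | Group: power at 84 | Interaction: power at 54 | Interaction: N for 80% |
|---|---|---|---|---|---|
| 0.4 | 0.64 | 78 | 0.83 | 0.96 | 34 |
| 0.5 | 0.60 | 86 | 0.79 | 0.98 | 28 |
| 0.6 | 0.56 | 96 | 0.75 | 0.996 | 24 |

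At rho 0.63, the highest implied value, the group effect has power 0.55 at 54 and needs 98.

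**Power at alpha 0.005.**
- Under the assumptions that reproduce 54: interaction at rho 0, 0.50; group effect at rho 0.10 to 0.12, 0.50 to 0.48.
- With 84 students at rho 0.4, 0.5 and 0.6: group effect 0.53, 0.47 and 0.42; interaction at least 0.97 throughout.

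**The case against.** A reader might infer that 54 is simply a wrong number, or that the trial was underpowered. The documents support neither.

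- **54 reproduces exactly from the stated inputs** for the interaction at rho = 0, so no arithmetic error is shown. This stands; the defect is in disclosure and in consistency.
- **The interaction may be the intended test.** The group main effect averages in the pre-test, taken before any training, and the abstract and sections 3.2 and 3.3 draw their conclusions from the interaction. For that term 54 is conservative at alpha 0.05, and even at 0.005 it gives 0.81 to 0.96 for rho 0.4 to 0.6. This stands too. But nothing in the plan ties Hypothesis 1 to the interaction, while its wording and the between-group focus in section 2.10 point towards the group comparison.
- **Near-zero rho is needed only if epsilon is 1.** The interaction formula also returns 54 at rho 0.2 with epsilon 0.75, and at rho 0.4 with epsilon 0.5. No such value is stated, and a sphericity check on the collected data does not show what was assumed at planning. The epsilon condition must therefore be attached to the finding.
- **The implied rho is post hoc and rough.** It did not exist when 54 was calculated. The two error terms disagree within each outcome, the variances rebuilt from the F values differ from those reported (knowledge 348 against 383, motivation 201 against 174), and the motivation post-test mean of 120.66 exceeds the scale maximum of 120 in section 2.2.3. This rules out replacing 54 with a figure derived from that rho. It does not rescue 54 for the group effect, since every implied value is well above 0.12.
- **The threshold of 0.005 may not be what was applied.** The abstract and sections 3.1 to 3.3 use p>0.05 for baseline non-significance. The two sections still have to be reconciled.

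**Conclusion.** The point holds conditionally, as a minor one. Section 2.3 omits the term, rho and epsilon, so the claim that 54 students give 80% power cannot be verified as written. If Hypothesis 1 is tested by the group main effect, the shortfall at 54 is 16 to 24 percentage points for rho 0.4 to 0.6, at f = 0.25 and alpha 0.05. If it is tested by the interaction, there is no shortfall at that alpha.

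The mismatch in alpha is a separate inconsistency that does not depend on the post hoc rho: the assumptions that yield 54 at 0.05 give about even odds of detection at 0.005.

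The practical consequence is small. The analysis used 84 students, close to or above 80% power for the group effect at 0.05 over most of the range, and the reported group, time and interaction effects have p<0.001, below either threshold. The results are not called into question on this ground.

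**What to change.** Revise the sample-size paragraph in section 2.3 and the significance statement in section 2.10:

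1. State one alpha and use it in both sections.
2. Name the ANOVA term that tests Hypothesis 1.
3. Disclose the rho and epsilon actually entered in the calculation.
4. Keep 54 as the planning record, and add that it does not give 80% power for the group main effect at rho 0.4 to 0.6.
5. Report the power of the 84 analysed students for the named term at the reconciled alpha. For the group effect at 0.05 this is 0.83, 0.79 and 0.75 at rho 0.4, 0.5 and 0.6; label this rho as a post hoc approximation from the reported F values, means and SDs.

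The cost is a few sentences. No further enrolment and no re-analysis is needed on this account. The price is a less favourable power statement if the group main effect is the named test.

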2.4. Inclusion and Exclusion Criteria

The inclusion criteria were as follows: (1) taking the Child Health and Nursing course for the first time, (2) having access to the internet and a computer or smartphone, (3) agreeing to take the concurrent courses on the Google Classroom platform, (4) agreeing to participate in the study voluntarily.

Exclusion criteria were as follows: (1) having previously received training in pediatric pain management, (2) withdrawing consent during the study, (3) failing to complete any stage of the intervention or data collection process.

[figure not shown]

Figure 2. CONSORT Flow Chart

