3.1. Intergroup Comparison of Descriptive Characteristics of Students

The descriptive characteristics of students in the intervention and control groups (n=84) are presented in Table 1. No significant differences were found between the groups in terms of age, gender, academic grade point average, and pain management self-assessment scores (p>0.05).

Table 1. Descriptive Characteristics of Students

Descriptive Characteristics	Intervention Group \(\overline{X} \pm SS \\ (Min - Max)		Control Group $\overline{X}\pm SS$ (Min – Max)		t	p
Age		9 ± 2.32 0–31)	21.86 ± 1.64 $(20-29)$		0.757	0.125
Pain management self- assessment (0-10 points)	4.52 ± 1.19 (2-7)		4.33 ± 1.05 (2-6)		0.776	0.333
Gender	n	%	n	%	Chi- square	p
Female	31	73.8	27	64.3	0.345	0.891
Male	11	26.2	15	35.7	0.343	
Academic grade point average						
2.00–3.00	21	50	21	50.0	0.001	1.00
3.01–4.00	21	50.0	21	50	0.001	
t: Independent samples t-test, chi-squa	are test					

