3.2. Findings Related to the Level of Knowledge About Pediatric Pain Management

According to the pre-test results, there was no significant difference between the intervention group and the control group in terms of pediatric pain management knowledge level (p > 0.05). However, according to the two-way mixed design ANOVA analysis, group effect (F=16.789, p < 0.001, η^2 =0.170), time effect (F=23.251, p<0.001, η^2 =0.221), and group*time interaction (F=27.834, p<0.001, η^2 =0.253) were found to be statistically significant. In particular, the significance of the group*time interaction indicates that the two groups showed different patterns of change in their knowledge levels over time (Table 2).

In the intervention group, a significant increase was observed in students' pediatric pain management knowledge scores. The mean score, which was 78.04 ± 18.79 in the pre-test, increased to 105.92 ± 23.62 in the post-test and was recorded as 92.26 ± 23.40 in the retention

test. The use of different letters (a, b, c) to denote the means obtained at different measurement times indicates statistically significant differences over time. However, in the control group that received education using the self-learning model, the knowledge level scores remained quite close to each other over time, and no significant change was detected (pre-test: 79.33±19.19, post-test: 78.09±14.68, retention test: 77.16±15.94). These findings indicate that the flipped classroom model is more effective than the self-directed learning model in improving knowledge levels in pediatric pain management and ensuring the retention of this knowledge (Figure 1).

Table 2. Pediatric Pain Management Knowledge Level Scores of the Intervention and Control Groups

Pediatric Pain Management	Intervention group (n=44)	Control group (n=44)	Statistic	Group	Time	Group*time interaction	
Knowledge Scale	Mean (SD)	Mean (SD)	Statistic				
Pre-test	78.04 (18.79) ^a	79.33 (19.19) ^a	F	16,789	23,251	27,834	
Post-test (4th week)	105.92 (23.62) ^b	78.09 (14.68) ^a	p	<0.001	<0.001	<0.001	
Retention Test (3rd month)	92.26 (23.40)°	77.16 (15.94) ^a	η^2	0.170	0.221	0.253	

a-c: Different letters indicate statistically significant groups within each column.

F: two-way mixed design analysis of variance; η^2 , partial eta square; SD, standard deviation.

[figure not shown]

Figure 1. Mean Scores of Pediatric Pain Knowledge by Group and Time

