3.3. Findings Related to Motivation Levels

Findings related to students' motivation levels are summarized in Table 3. There was no significant difference in motivation level scores between students in the intervention group and those in the control group in the pre-test (p > 0.05). However, when the results of the two-way mixed design ANOVA were examined, group effect (F=39.206, p < 0.001, η^2 =0.323), time effect (F=67.749, p<0.001, η^2 =0.452), and group*time interaction (F=70.240, p<0.001, η^2 =0.461) were found to be statistically significant. The significance of the group*time interaction indicates that the effect of the time factor on motivation levels is not the same for both groups (Table 3).

In the entrepreneurial group that received education with the flipped classroom model, a significant increase was observed in students' motivation scores. The average score, which was 83.61 ± 12.61 in the pre-test, increased to 120.66 ± 17.20 in the post-test and was recorded as 101.50 ± 12.26 in the retention test. The use of different letters (a, b, c) to denote the averages at different measurement times indicates statistically significant differences over time. In contrast, the motivation level scores of the control group, which received education using the self-learning model, remained quite close to each other at all time points, and no significant change was observed (pre-test: 86.76 ± 12.03 , post-test: 86.40 ± 11.91 , retention test: 85.61 ± 12.36). These findings indicate that the flipped classroom model is more effective than the self-directed learning model in enhancing students' motivation (Figure 2).

Table 3. Learning Motivation Scores of the Intervention and Control Groups

Motivation Survey Regarding Teaching	Intervention group (n=44) Mean (SD)	Control group (n=44) Mean (SD)	Statistic	Group	Time	Group*time interaction
Materials Pre-test	83.61 (12.61) ^a	86.76 (12.03) ^a	F	39,206	67,749	70,240
Post-test (4th week)	120.66 (17.20) ^b	86.40 (11.91) ^a	p	<0.001	<0.001	<0.001
Retention Test (3rd month)	101.50 (12.26)°	85.61 (12.36) ^a	η^2	0.323	0.452	0.461

a-c: Different letters indicate statistically significant groups within each column.

F: Two-way mixed design analysis of variance; η^2 , partial eta square; SD, standard deviation.

[figure not shown]

Figure 2. Mean Scores of Learning Motivation by Group and Time

4. Discussion

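### Exclusion criteria 2 and 3 remove students for events after randomization, with no all-randomized set or missing-data rule; separately, the n=44 table headings conflict with the 42 per arm analysed

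*Combined protocol and SAP*

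**What the plan says.** Section 2.4 gives three exclusion criteria. The first, earlier training in pediatric pain management, can be checked at entry. The second is "withdrawing consent during the study" and the third is "failing to complete any stage of the intervention or data collection process".

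Section 2.10 names the software, the tests and the assumption checks, with a two-way mixed ANOVA for group, time and their interaction. It does not say which students enter the analysis or how an absent score is handled. Its closing statement, "All analyses were designed to focus on between-group comparisons", says what is compared but not in whom. The only reference to loss is in the sample-size paragraph of section 2.3, which allows for it without giving a rate.

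The counts are given in two ways:

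- Abstract: "A total of 84 third-year nursing students were randomly assigned to an intervention (n=42) and control (n=42) group".
- Section 3.1: "The descriptive characteristics of students in the intervention and control groups (n=84) are presented in Table 1".
- Section 2.3: "the study was conducted with 44 participants in each group".
- Tables 2 and 3: both arms are headed n=44.

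**The concern.** An exclusion criterion should describe a condition present before randomization. A criterion that depends on finishing the course and all the questionnaires selects students by what happened after they were assigned, and the balance that randomization provides no longer covers those who remain.

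The stages to be completed differ by arm. The intervention arm had weekly interactive online sessions (section 2.6). The control arm watched videos individually and did assignments (section 2.7). Those who fall out could therefore differ between arms. Learning motivation is the secondary outcome and plausibly affects who finishes. Blinding the statistician (section 2.3) does not correct a selection made before the data set was handed over.

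The conflicting counts make this harder to judge. If 44 per arm entered and 42 were analysed, students were removed and the rule mattered. If 42 per arm were randomized and all were analysed, it did not. The text and tables do not say which.

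**Working it through.** **1. Can the criteria act before assignment?** Withdrawal during the study, a missed intervention stage, and a missed post-test or retention test all come after assignment. A missed pre-test is the one possible exception: section 2.8 places the pre-test before the training but does not say whether it came before randomization.

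**2. Does anything restore the excluded students?** No. Section 2.10 has no all-randomized set, no missing-data rule and no sensitivity analysis. A standard mixed ANOVA drops any student who lacks one of the three scores.

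**3. How many students are behind Tables 2 and 3?** Partial eta-squared follows from F and its degrees of freedom:

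eta² = F·df1 / (F·df1 + df2)

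For the group effect, df1 = 1 and df2 = N − 2. For time and interaction, df1 = 2 and df2 = 2(N − 2). Example, knowledge group effect at N=84: 16.789 / (16.789 + 82) = 0.1699.

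| Effect | F | Printed eta² | N=84 | N=88 |
|---|---|---|---|---|
| Knowledge, group | 16.789 | 0.170 | 0.1699 | 0.163 |
| Knowledge, time | 23.251 | 0.221 | 0.2209 | 0.213 |
| Knowledge, interaction | 27.834 | 0.253 | 0.2534 | 0.245 |
| Motivation, group | 39.206 | 0.323 | 0.3235 | 0.313 |
| Motivation, time | 67.749 | 0.452 | 0.4524 | 0.441 |
| Motivation, interaction | 70.240 | 0.461 | 0.4614 | 0.450 |

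All six agree at N=84. None agrees at N = 82, 83, 85, 86 or 88.

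**4. Are the printed means possible?** Both scales are sums of integer items, so each mean is a whole-number total divided by n. At n=42 all 12 means in Tables 2 and 3 can be reached if they were truncated to two decimals. At n=44 four cannot be reached by rounding or truncation: 105.92, 92.26, 79.33 and 86.76. For example, 4660/44 = 105.91 and 4661/44 = 105.93, whereas 4449/42 = 105.928. (This checks divisibility only. The motivation post-test mean of 120.66 exceeds the scale maximum of 120 in section 2.2.3, which is a separate matter.)

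**5. Table 1.** The self-assessment t is (4.52 − 4.33) / √((1.19² + 1.05²)/n). This gives 0.776 at n=42, as printed, and 0.794 at n=44. The proportions of women, 31/42 = 73.8% and 27/42 = 64.3%, match the table; with 44 they would be 70.5% and 61.4%. So the baseline table also rests on 42 per arm.

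**6. Possible losses.** If 84 were randomized, 0 were lost. If 88 entered, 4/88 = 4.5% were lost, two in each arm.

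**7. What four losses could do (illustration).** Assume 44 per arm were randomized and two per arm removed. Each arm's mean becomes (42·m + 2·v)/44, where m is the printed mean and v the value given to the removed students. The t values are unadjusted two-sample tests on the knowledge score.

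| Value given to removed students | Post-test difference | Retention difference |
|---|---|---|
| None (as printed) | 27.83 | 15.10 |
| Own arm's pre-test mean (78.04; 79.33) | 26.51 (t = 6.33) | 14.36 (t = 3.42) |
| Scale extremes against the intervention (29; 145) | 21.29 (t = 4.08) | 9.14 (t = 1.79, p = 0.077) |

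These are bounds under an assumption, not estimates of bias.

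**The case against.** The strongest reply is that nobody may have been lost. The abstract states that 84 were randomly assigned, section 2.1 reports no interruption of education or follow-up, and Table 1 has exactly 21 students in each stratum-by-arm cell. The reading with 88 entered contradicts the abstract's count and needs four losses that leave all four cells at 21. This carries weight, and the visible text leans towards no loss. But no attrition count is given, and section 2.3 says plainly that the study was run with 44 per group.

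A second reply is that the CONSORT flow chart may already give the numbers. It is not visible in the text available for this review and cannot be called missing. Even a complete chart would leave section 2.3 and the headings of Tables 2 and 3 in conflict with the abstract, and would leave the completion rule in section 2.4.

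Third, four losses could hardly overturn the result. That is largely true: in the illustration the post-test difference survives even the scale extremes, and only the retention comparison loses significance there. This limits the seriousness of the point without removing it.

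Finally, criterion 2 may be mostly a matter of labelling, since scores from students who withdrew consent may be unusable. That stands. Criterion 3 is the substantive one.

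**Conclusion.** Both parts hold. The plan as written defines a completers-only comparison, with no all-randomized set and no missing-data rule. The n=44 headings of Tables 2 and 3 are wrong by 2 per arm, because the printed statistics come from 84 students. That second conclusion rests only on the F values, effect sizes and means in the document.

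Whether the completion rule altered any estimate is not known. The two readings give 0 of 84 or 4 of 88 (4.5%) lost, and the count conflict does not by itself show that students were dropped. The direction of any bias is unknown, and its size cannot be computed without the excluded students' data. This should be fixed, but nothing here shows that the main finding is wrong.

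**What to change.** - Change the headings of Tables 2 and 3 to n=42 and reconcile section 2.3 with the abstract.
- State for each arm the numbers randomized, excluded (with reasons) and analysed, and make text, tables and flow chart agree.
- In section 2.4 keep only conditions that can be established before randomization. Report criteria 2 and 3 as withdrawal and missing data.
- In section 2.10 define the primary set as all randomized students in their assigned arm, and state how missing scores are handled.
- If anyone was lost, reanalyse with a likelihood-based repeated-measures model using every available score that consent allows. Keep the completers analysis as a sensitivity analysis, and say that the change was made after the results were known.
- If no one was lost, say so. No reanalysis is then needed.

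With no losses the cost is corrected counts and headings, revised wording in sections 2.4 and 2.10, and one sentence stating that none occurred. With losses it is a small reanalysis of existing data, limited by whatever scores withdrawn consent makes unusable.
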